5.8 Data and Safety Monitoring Board

An independent Data and Safety Monitoring Board (DSMB) will be informed of all serious adverse events and any unanticipated adverse device events that occur during the study and will review compiled safety data at periodic intervals.

We will implement a system to oversee and monitor our randomized clinical trial to ensure the safety of participants, as well as the validity and integrity of the data. We will establish a data safety monitoring board, ensuring that the DSMB's responsibilities are commensurate with the risks, complexity, and nature of our studies. We will define the role of the DSMB prior to initiating the clinical trial and clearly delineate the operating procedures and policies of the board, including "stopping rules" for the study.

Membership: Our DSMB will be comprised of experts in diverse scientific disciplines to ensure participant safety and help interpret the data in our studies.

Meetings: Prior to implementation of the study, the DSMB will meet to review the consent and protocol, making recommendations for any needed changes. For this meeting, study investigators will be on hand to answer any specific questions. After the initial meeting, the DSMB will plan to meet in-person or by conference call once yearly. DSMB members will have the ability to request more frequent reviews or meetings at any time during the study if they determine such reviews could help ensure patient safety or data integrity. The DSMB may meet in "closed session," and they may periodically ask study investigators to attend a meeting to provide additional details on the implementation or conduct of the trial or other pertinent information. After its initial meeting, the DSMB will review the implementation and progress of the study, evaluating study data in both individual and aggregate form to detect evidence of significant benefit or harm for participant while the trial is in progress. This latter review, beyond that provided by the IRB, serves as a means of additional human subject protection. It does not supplant the regulatory requirement for the principal investigator to report serious and unanticipated adverse events to the local IRB or relevant regulatory bodies.

Summary of DSMB duties: The DSMB will perform the following activities: 1) Review of the research protocol and plans for data and safety monitoring; 2) Evaluate the progress of the intervention trial, including periodic assessments of data quality and timeliness, participant recruitment, accrual and retention, participant risk versus benefit, and other factors that could potentially affect study outcome; 3) Protect the confidentiality of the trial data and the results of monitoring; and 4) Make recommendations to the investigators concerning continuation, modification, or termination of the trials. The DSMB also has the right to make independent representation to the regulatory bodies (NIH, IRB) if there has been any failure in reporting by the principal investigator. The DSMB can also instruct the principal investigator to pause or terminate pursuance of research if there is a breach in regulatory guidelines or good clinical practices. If the DSMB notes serious and unexpected adverse events, or unanticipated problems involving risks to participants or others, which are related to the study, the PI will be notified immediately in writing.

To assist the DSMB in their duties, the investigators will prepare a report prior to each DSMB meeting, including issues related to participant recruitment (consent, enrollment, dropout), data collection (e.g., quality, timeliness, completeness, security), outcome analyses, and all serious and unexpected adverse experiences. The investigators will also notify the DSMB of any significant study modifications, emphasizing any changes made in response to adverse events (see definition below)

After the DSMB meeting, the DSMB will issue a report summarizing their findings. More specifically, they will provide commentary on participant recruitment, consent, and drop out; the quality, timeliness, and completeness of data collection; outcome analyses that help determine whether a study should continue; and all serious and unexpected adverse experiences. In each area (e.g., participants consent), they will recommend any necessary changes in study policies or

protocol and explain how the changes will help ensure participant safety or data integrity. These reports will be kept by the PI, who will file them with the local IRB.

This application includes a trial that requires registration in ClinicalTrials.gov.

5.9 Potential Risks and Side Effects

5.9.1 Venipuncture Risks

A hollow needle/plastic tube will be placed in the arm for taking blood samples. Blood draws can cause some common reactions like pain, bruising, or redness at the sampling site. Less common reactions include bleeding from the sampling site, formation of a small blood clot or swelling of the vein and surrounding tissues, and fainting.

5.9.2 Fingerstick Risks

About 1 drop of blood will be removed by finger stick for measuring blood sugars and sometimes HbA1c or other tests. This is a standard method used to obtain blood for routine hospital laboratory tests. Pain is common at the time of lancing. In about 1 in 10 cases, a small amount of bleeding under the skin will produce a bruise. A small scar may persist for several weeks. The risk of local infection is less than 1 in 1000. This should not be a significant contributor to risks in this study as finger pokes are part of the usual care for people with diabetes.

5.9.3 Subcutaneous Catheter Risks (Continuous Glucose Sensor)

Subjects using the continuous glucose sensor will be at low risk for developing a local skin infection at the site of the sensor needle placement. There may be bleeding where the catheter is put in and bleeding under the skin causing a bruise (1 in 10 risk).

Study staff should verbally alert the subject that on rare occasions, the continuous glucose sensor may break and leave a small portion of the sensor under the skin that may cause redness, swelling or pain at the insertion site. The subject should be further instructed to notify the study coordinator immediately if this occurs.

5.9.4 Risk of Hypoglycemia

As with any person having insulin-dependent diabetes, there is always a risk of having a low blood sugar (hypoglycemia). The frequency of hypoglycemia should be no more and possibly less than it would be as part of daily living. Symptoms of hypoglycemia can include sweating, jitteriness, and not feeling well. Just as at home, there is the possibility of fainting or seizures (convulsions) and that for a few days patients may not be as aware of symptoms of low blood sugar.

5.9.5 Risk of Hyperglycemia

Hyperglycemia and ketonemia could occur if insulin delivery is attenuated or suspended for an extended period or if the pump or infusion set is not working properly. A sensor which was functioning poorly and significantly under-reading glucose values could lead to inappropriate suspension of insulin delivery.

5.9.6 Risk of Device Reuse

The Dexcom CGM is labeled for single use only. The sensor (the component of the system that enters the skin) will be single use only. The transmitter and receiver will be reused after cleaning as described below. The transmitter is attached to the sensor but does not enter the skin and the receiver is a hand held device. The transmitter and receiver will be cleaned adhering to hospital protocol as described below. Subjects will be informed that the FDA has approved these devices for single use and that by using them among multiple patients, bloodborne pathogens (i.e. Hepatitis B) may be spread through the use of multiple users.

The Accu-Chek Combo System and Tandem t:slim X2 insulin pump are labeled for single-patient use. The Accu-Chek Combo system is comprised of the Accu-Chek Spirit Insulin Pump and the Aviva Combo Device. The Aviva Combo device when used as a glucometer will be single patient use at all times. The Accu-Chek Spirit Insulin Pump itself is handheld and is not a glucometer. The subject interactions are primarily with the AP system interface and the Aviva Combo device, not with the Accu-Chek Spirit Insulin Pump menu interface itself. The Accu-Chek Spirit Insulin Pump handheld device and the Tandem t:slim X2 insulin pump will be reused after cleaning adhering to hospital protocol as described below. All infusion set equipment will be single patient use only (infusion set insertion kits, tubing, cartridges etc.)

Cleaning Procedure: Equipment that touches intact skin will be cleaned with ethyl or isopropyl alcohol (70-90%), quaternary ammonium germicidal detergent (i.e. CaviCide) or household bleach. The contact time on the surface depends on the method used to clean the equipment. CaviCide requires three minutes on the surface. Clorox Germicidal Bleach Wipes require two minutes on the equipment. The surface should remain wet (i.e. slightly damp) with the disinfectant to be considered effective though not wet enough to leave drops of liquid. Equipment will be stored in a clean zipped bag.

Hb1Ac Risk: The University of Virginia central labs have College of American Pathologist (CAP) and the Clinical Laboratory Improvement Amendments (CLIA) certifications. While the central lab is not NGSP certified, the calibrators for the HbA1c assay are traceable to NGSP. The equipment (Tosoh G7) is NGSP certified. An NGSP Point of Care analyzer (i.e. DCA Vantage Analyzer) may also be utilized at the research site to obtain the subject's HbA1c level.

5.9.7 Other Risks

Some subjects may develop skin irritation or allergic reactions to the adhesives used to secure the CGM, or to secure the insulin infusion sets for the CSII. If these reactions occur, different adhesives or "under-taping" (such as with IV 3000, Tegaderm, etc.) will be tried, sites will be rotated frequently, and a mild topical steroid cream or other medication may be required.

Whenever the skin is broken there is the possibility of an infection. The CGM and pump infusion sites are inserted under the skin. It is possible that any part that is inserted under the skin may cause an infection. These occur very infrequently, but, if an infection was to occur, oral and/or topical antibiotics can be used. The risk of skin problems could be greater if a sensor is used for

longer than manufacturer recommendations. Therefore, participants will be carefully instructed about proper use of the sensor.

Data downloaded from the CGM, pump, and the home glucose and ketone meter will be collected for the study as measures of diabetes self-management behaviors. Some people may be uncomfortable with the researchers' having such detailed information about their daily diabetes habits.

Loss of confidentiality is a potential risk; however, data are handled to minimize this risk.

5.10 Study Stopping Criteria

5.10.1 Criteria for Individual Subjects

Rules for stopping the study for an individual subject are as follows:

- 1. System or controller malfunctions that impose on the safety of the subject, unless the problem can be clearly identified and the system definitively repaired
- 2. Two distinct episodes of severe hypoglycemia or hyperglycemia/DKA (not associated with infusion set failure) as defined in section 5.1 related to automated insulin delivery during closed loop use
- 3. The subject requests the study be stopped
- 4. Subject pregnancy
- 5. Use of oral or injectable glucocorticoids during closed-loop system operation (subject may resume study procedures once effects of glucocorticoids are no longer present)
- 6. Study staff are persistently unable to contact the subject in a timely manner during the course of the study
- 7. Persistent subject non-adherence to safety-related procedures such as frequency of fingersticks or hypoglycemia, hyperglycemia and ketone treatment instructions
- Ketones ≥ 3 mmol/L or with symptoms requiring action regardless of blood sugar or ketones (i.e. abdominal pain, vomiting illness, unable to eat or drink, fever ≥ 101.5, clinical need for Tylenol/acetaminophen, significant illness, use of epinephrine). Subject may resume study procedures once conditions or symptoms are no longer present.

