3.2 Randomization

A subject who meets all the inclusion and exclusion criteria will be enrolled in the study. After completion of the eligibility criteria, the participant will be randomized to one of the two arms: Group A and Group B as described and illustrated in Figure 1.

Subjects who are randomized to Group A will start SAP within four weeks of completing Visit 2; Visit 3 and Visit 4 will occur following completion of SAP.

Subjects who are randomized to Group B will proceed directly to Visit 2, Visit 3 and 4.

All training and run-in visits were structured to accommodate subjects who are experienced with the system or system components as well as subjects who have little to no experience with the system or system components. As a result, training/run-in visits may be combined as described in the protocol depending on the skill level of the individual subject.

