The subject must be able to complete system-related tasks independently to be eligible to continue in the study.

3.6 Visit 5 - AP System Run-In phase: Home Use in Pump Only (Open Loop) Configuration

Eligible subjects who have not had recent use of the system (more than ~2 weeks of use in the past 6 months or more than ~2 months of use in the past year) will complete up to 2-week home use period with the full system in pump only (open loop) configuration where no closed loop algorithms are activated. Subject will be instructed not to start closed loop during this run-in phase. Subjects who have had prior experience with the AP system as defined above will not be required to do Visit 5. Subjects who are demonstrating proficiency, as determined by the study physician, may have a shorter open loop run-in phase with a minimum of 5 days duration Criteria for proficiency is listed in section 3.11.

For the inControl system, remote monitoring will be available during this period for the purposes of data collection and ad hoc assessment of system performance by study team. The study team will be available for the subject to contact during this phase. Study staff will contact the subject and review data on the Remote Monitoring once daily. The subject may contact the study staff at any time.

For the Tandem-G6 system, remote monitoring will not be available. Study staff will contact the subject daily to assess difficulties with the use of the system. The subject may contact the study staff at any time. If the study team requires additional information, the subject may be asked to upload the pump at home so that the study can review data on the t:connect website.

3.7 Visit 6 + Visit 7 + Visit 8 Washout Following Completion of the Each Study Phase

At the completion of the each phase of the study, subjects will have up to a two week washout prior to proceeding to the next phase.

First Phase: Group A 8 weeks of SAP; Group B 8 weeks of USS +SAP(d) Second Phase: Group A 8 weeks of USS +SAP(d); Group B 8 weeks of USS + CLC(d) Third Phase: Group A 8 weeks of USS + CLC(d); Group B 8 weeks of USS +SAP (d) Fourth Phase: Group A 8 weeks of USS + SAP(d); Group B 8 weeks of SAP

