3.9 Study Procedures during SAP

- Study subjects will be using the study CGM (Dexcom G4) and either their home pump or study pump for 8 weeks. Subjects using the Tandem-G6 system during AP phases will use their home pump during SAP.
- Subjects will be following their usual home insulin parameters. There are no predictive algorithms running for insulin administration.
- Subjects will be requested to use their personal glucometer or study glucometer for all fingersticks including CGM calibrations.
- Subjects will perform their usual activities and manage their diabetic regimen per their usual routine.
- Study staff will be available at any time for the study subject to contact.
- Staff will contact the subject once a month after the first month.

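### Rules 1 and 2 of section 5.10.1 end study participation, not only AP use, so a stop during AP use removes the SAP phase in Group B and never in Group A

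*Combined protocol and SAP*

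**What the plan says.** The individual stopping rules in 5.10.1 are introduced by "Rules for stopping the study for an individual subject are as follows". Rule 1 covers malfunctions that affect safety, "unless the problem can be clearly identified and the system definitively repaired". Rule 2 covers two distinct severe hypoglycemic or hyperglycemic/DKA episodes "related to automated insulin delivery during closed loop use". Rule 5 (glucocorticoids) and the ketone/illness rule each add that the subject may take up study procedures again; rules 1 and 2 do not.

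On phase order, section 3.2 says of Group A that "Visit 3 and Visit 4 will occur following completion of SAP". Section 3.7 puts SAP last for the other group: "Fourth Phase: Group A 8 weeks of USS + SAP(d); Group B 8 weeks of SAP". During SAP, section 3.9 states: "There are no predictive algorithms running for insulin administration".

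Outcome visits (HbA1c, questionnaires, device downloads) follow completed phases in 3.7 and 3.8. After discontinuation, 5.2 follows only adverse events that are still continuing.

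The Specific Aim 1 primary outcome in 6.1 compares CGM time below 70 mg/dL on USS+SAP(d) with SAP alone, without a rise in HbA1c, by repeated measures ANOVA. The overall analysis is intention-to-treat with mixed models. Section 6.1 gives no rule for a missing phase.

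**The concern.** SAP is the comparator in the Specific Aim 1 primary contrast. A subject who never reaches SAP gives no within-subject pair to a repeated measures ANOVA. A mixed model can still use that subject's USS+SAP(d) data, but the comparator remains unobserved.

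The subjects lost this way would have had severe events or unrepaired malfunctions on the AP system. The missingness is therefore related to treatment, and the sequence order confines the loss of SAP to Group B. It is also largely avoidable: SAP runs no control algorithm, so the automated delivery behind a rule 2 stop plays no part in it. Dropping the phase by rule fits poorly with an intention-to-treat approach.

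**Working it through.** **Inputs.** Sequences from 1.1 and 3.7, with N = USS+SAP(d) and D = USS+CLC(d): Group A is SAP, N, D, N; Group B is N, D, N, SAP. From 6.2: 110 randomized, 76 completing, attrition up to 31%. These agree: 110 × 0.69 = 75.9, and 110 − 76 = 34. They are used here only for scale; the sample size is not challenged.

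**Does a stop end participation?** Rule 3 uses the same object as the heading: the subject asks for the study to be stopped. Where a stop is meant to be temporary, 5.10.1 says that study procedures may resume. Where only closed loop is to be avoided, as during illness in 3.10, the protocol says that. Rules 1 and 2 have neither kind of wording.

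**Enumeration.** For each position at which AP use can be stopped, count which phases are already complete. Rule 2 needs closed loop, so only rule 1 can apply in the Visit 5 open-loop run-in (3.6).

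| Group and stop position | Completed before | SAP kept | N/SAP pair kept |
|---|---|---|---|
| A, Visit 5 run-in | SAP | yes | no |
| A, phase 2 | SAP | yes | no |
| A, phase 3 | SAP, N | yes | yes |
| A, phase 4 | SAP, N, D | yes | yes |
| B, Visit 5 run-in | none | no | no |
| B, phase 1 | none | no | no |
| B, phase 2 | N | no | no |
| B, phase 3 | N, D | no | no |

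- AP phases only: SAP kept 3/3 in A and 0/3 in B; pair kept 2/3 and 0/3.
- With the run-in: SAP kept 4/4 and 0/4; pair kept 2/4 and 0/4.
- If Group B's SAP phase is retained, run-in and phase 1 stops give SAP without a pair, and phase 2 and 3 stops give a pair. Group B becomes 3/3 and 2/3, or 4/4 and 2/4 with the run-in. These equal the Group A counts.

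**Size.** The documents give no stop rate. Assumptions: 0 to 2 stops in total, with 4 as an upper illustration; an even split between groups; 55 per group; each AP phase equally likely.

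- Pairs lost per stop: A 1/3 = 0.33; B 1.
- Two stops (one per group): 0.33 pairs lost in A, 1 in B; gap 1 − 0.33 = 0.67.
- Four stops (two per group): 0.67 in A (0.67/55 = 1.2%), 2 in B (2/55 = 3.6%); gap 1.33.
- If the run-in counts as a fourth equally likely position, A loses 2/4 = 0.5 per stop, so the gap per stop in each group is 0.5.
- For scale: 2/110 = 1.8% and 4/110 = 3.6% of subjects; 2/34 = 5.9% and 4/34 = 11.8% of planned attrition.

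The SAP-phase result does not depend on the weights. The pair counts do, and equal weights are crude because USS+CLC(d) runs closed loop for 24 hours and USS+SAP(d) only from evening to morning.

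**The case against.** The strongest reply is that this hardly matters. Rule 2 needs two severe, related episodes under the strict definitions in 5.1; rule 1 lapses on repair; section 2.2.2 excludes people with recent DKA admission or severe hypoglycemia with seizure or loss of consciousness; and 5.10.2 suspends the study once device-related events occur in more than two subjects. Ordinary dropout with SAP last is a larger source of missing SAP data, and this change does not touch it, nor stops under rules 3 and 7. All of that stands and limits the point to an optional improvement. Section 5.10.2 is not a cap, however, since the study may resume.

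Three further objections stand in part.

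- A reader might infer that the protocol expressly withholds SAP after a stop. It never says so; the reading rests on the heading, the missing resume clauses and the absence of any follow-up provision. If the intent was narrower, the amendment simply records it.
- A reader might infer that the cause of any rule 1 or 2 stop is absent from SAP. This holds for rule 2. For rule 1 it is not settled: section 1.4 lists the CGM and pump as system components, and 3.9 has SAP on the study CGM with a home or study pump. Only for one configuration does it say "Subjects using the Tandem-G6 system during AP phases will use their home pump during SAP".
- Group B's recovered SAP data would follow a severe event or malfunction, whereas Group A's SAP precedes the AP phases. Equality with Group A is equality of phase counts only.

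Ending participation after repeated severe events is a defensible safety choice. The proposal keeps that option through the investigator's judgement.

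**Conclusion.** The point holds as a structural one. As worded, rules 1 and 2 end participation, and the phase order makes a stop during AP use cost the SAP comparator in Group B every time and in Group A never. Pairs survive in 2 of 3 AP-phase positions against 0 of 3, or 2 of 4 against 0 of 4 with the run-in.

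The number affected is probably very small and is assumed, not documented. A reader might go on to infer a biased Specific Aim 1 estimate or an underpowered trial. The documents support neither: they give no stop rate from which to compute a shift, and the illustrations above amount to a gap of about one pair among 110 subjects.

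Limits: the counts are of completed phases, so partial data from an interrupted phase are ignored. The CGM run-in of up to two weeks is not counted as an SAP phase. Up to four pilot subjects (3.1.1) may meet closed loop at a time that is not stated.

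**What to change.** Keep every trigger in 5.10.1, the DSMB review and 5.10.2. Add to 5.10.1 that rules 1 and 2 end closed-loop/AP use but not study participation, unless the subject withdraws consent or the investigator judges further participation unsafe. Then:

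- Group B subjects stopped this way do their assigned 8-week SAP phase, with its planned HbA1c, questionnaires and CGM download, and those data enter the planned mixed model.
- If a rule 1 malfunction involves the study CGM or pump, replace that component before SAP, or use the home pump.
- Report rule 1 and 2 stops by group.

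The fix does not require leaving post-stop assigned AP periods out of the main contrast; that is a separate and debatable analysis choice.

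Cost: a short amendment to 5.10.1 with matching lines in 3.7 and 6.1, IRB submission, notice to the DSMB and any FDA step this IDE study needs, best bundled with another amendment. SAP visits and CGM supplies are already planned for these subjects. The downsides are follow-up of a few more subjects, and Group B SAP data that may reflect changed behaviour after a severe event.
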